5.5.3 All cohorts

- Previous and concomitant medication

Previous medication is defined as medication with at least one dose taken before the date of the first dose of study drug (exclusive).

Concomitant medication is defined as medication with at least one dose taken between the date of first dose (inclusive) and the date of last dose plus 30 days (inclusive) of study drug.

- Previous and concomitant non-medication therapy

Previous non-medication therapy is defined as non-medication therapy administered at least once before the date of the first dose of study drug (exclusive).

Concomitant non-medication therapy is defined as non-medication therapy administered at least once between the date of first dose (inclusive) and the date of last dose plus 30 days (inclusive) of study drug.

- Ophthalmologic assessment (visual acuity measurement, slit lamp biomicroscopy, tonometry and dilated fundus examination)

6 STATISTICAL METHODOLOGY

6.1 General Considerations

Continuous data will be summarized descriptively including the number of subjects (n), mean, standard deviation (SD), median, minimum and maximum. When needed, the use of other percentiles (e.g., 10%, 25%, 75%, 90%) will be specified in the relevant section. In addition, for plasma (MMAE) and serum concentrations, the coefficient of variation, the geometric mean and the coefficient of variation for geometric mean will also be calculated. Categorical data will be summarized by frequencies and percentages. Percentages by categories will be based on the number of subjects with no missing data, i.e., the percentages for the nonmissing categories will add up to 100%.

Unless otherwise specified, confidence intervals (CIs) will be calculated at two-sided 95% level. For time-to-event endpoints, median survival time will be estimated using Kaplan-Meier method, with 2-sided 95% CI.

Baseline value is defined as the last nonmissing measurement prior to the first dose of study drug unless specified otherwise. In general, data will be summarized by cohort and overall.

All data summarization and analyses will be performed using SAS® Version 9.4 or higher on Red Hat Enterprise Linux. Specifications for table, figures, and data listing formats can be found in the TLF specifications.

6.2 Study Population

6.2.1 Disposition of Subjects

The following subject data will be presented:

- Number and percentage of subjects with informed consent, discontinued before enrollment, and enrolled will be summarized for all subjects with informed consent for overall only;
- Number and percentage of subjects included in each analysis set will be summarized by cohort and overall for all enrolled subjects;
- Number and percentage of subjects discontinued treatment, and the primary reason for treatment discontinuation will be summarized by cohort and overall for FAS;
- Number and percentage of subjects completed or discontinued 30-day safety follow-up, and the primary safety follow-up status will be summarized by cohort and overall for FAS;
- Number and percentage of subjects discontinued post treatment follow-up, and the primary post treatment follow-up status will be summarized by cohort and overall for FAS;
- Number and percentage of subjects discontinued long-term follow-up and the primary long-term follow-up status will be summarized by cohort and overall for FAS; and
- Number and percentage of subjects completed or discontinued the screening period and the primary screening status will be summarized for all subjects with informed consent for overall only.

6.2.2 Protocol Deviations

Protocol deviations as defined in the study protocol [Section 10.3 Major Protocol Deviations] will be assessed for all enrolled subjects. The number and percentage of subjects with the following protocol deviation criteria will be summarized for each criterion and overall, by cohort and overall as well as by investigative site. Subjects deviating from a criterion more than once will be counted once for the corresponding criterion. Subjects with more than one protocol deviation will be counted once for the overall summary. A data listing will be provided by site and subject. The protocol deviation criteria will be uniquely identified in the summary table and listing.

The unique identifiers will be as follows:

PD1 - Entered into the study even though they did not satisfy entry criteria.

PD2 - Developed withdrawal criteria during the study and was not withdrawn.

PD3 - Received wrong treatment or incorrect dose. For enfortumab vedotin, incorrect dose will be defined as less than or greater than 10% from the intended dose, i.e., less

than 90% of the intended dose or greater than 110% of the intended dose. For pembrolizumab, any dose of 1000 mg or greater will be considered incorrect dose.

PD4 - Received excluded concomitant treatment.

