6.1.2 Pembrolizumab (Cohort 9 Only)

Pembrolizumab injection is a sterile, preservative-free, clear to slightly opalescent, colorless to slightly yellow solution that requires dilution for IV infusion. Each vial contains 100 mg of pembrolizumab in 4 mL of solution. Each 1 mL of solution contains 25 mg of pembrolizumab and is formulated in L-histidine (1.55 mg), polysorbate 80 (0.2 mg), sucrose (70 mg), and Water for Injection, United States Pharmacopeia (USP). Pembrolizumab will be administered as a dose of 200 mg using a 30-minute intravenous infusion on day 1 of each 3-week cycle, approximately 30 minutes after completion of the enfortumab vedotin administration. Sites should make every effort to target infusion timing to be as close to 30 minutes as possible. However, given the variability of infusion pumps from site to site, a window between -5 minutes and +10 minutes is permitted (i.e., infusion time is 30 minutes (-5 min/+ 10 min)).

Pembrolizumab may be administered for a maximum of 35 cycles.

The pharmacy manual contains specific instructions for the preparation of the pembrolizumab infusion and administration of infusion solution.

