6.4 Investigational Product Compliance

The dose and schedule of enfortumab vedotin and pembrolizumab administered to each subject will be recorded on the eCRF for each dose. Reasons for dose delay, reduction or omission will be documented. Dosing noncompliance for enfortumab vedotin of less than or greater than 10% from each intended dose will be considered a major protocol deviation. Dosing noncompliance for pembrolizumab of 1000 mg or greater will be considered a major protocol deviation.

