6.6.2 Pembrolizumab

6.6.2.1 Dose Modification and Toxicity Management for Immune-mediated AEs Associated with Pembrolizumab

AEs associated with pembrolizumab exposure may represent an immunologic etiology. These imAEs may occur shortly after the first dose or several months after the last dose of pembrolizumab treatment and may affect more than one body system simultaneously. Therefore, early recognition and initiation of treatment is critical to reduce complications. The dose of pembrolizumab should not be reduced. Based on existing clinical study data, most imAEs were reversible and could be managed with a delay of pembrolizumab, administration of corticosteroids and/or other supportive care. For suspected imAEs, ensure adequate evaluation to confirm etiology or exclude other causes. Additional procedures or tests such as bronchoscopy, endoscopy, skin biopsy may be included as part of the evaluation. Based on the severity of imAEs, withhold or permanently discontinue pembrolizumab and administer corticosteroids. Dose delay and toxicity management guidelines for imAEs associated with pembrolizumab are provided in [Table 9]. Participants who experience unacceptable toxicity that is clearly attributable only to enfortumab vedotin may continue on pembrolizumab monotherapy up to a maximum of 35 cycles.

Table 9 Dose Modification and Toxicity Management Guidelines for Immune-mediated AEs Associated with Pembrolizumab

General instructions:

1. Severe and life-threatening imAEs should be treated with IV corticosteroids followed by oral steroids. Other immunosuppressive treatment should begin if the imAEs are not controlled by corticosteroids.
2. Pembrolizumab must be permanently discontinued if the imAE does not resolve or the corticosteroid dose is not ≤ 10 mg/day within 12 weeks of the last pembrolizumab treatment.
3. The corticosteroid taper should begin when the imAE is \leq grade 1 and continue at least 4 weeks.
4. If pembrolizumab has been withheld, pembrolizumab may resume after the imAE decreased to \leq grade 1 after corticosteroid taper.

Immune-mediated AEs	Toxicity grade (NCI-CTCAE V5.0)	Action with Pembrolizumab	imAE Management with Corticosteroid and/or Other Therapies	Monitoring and Follow-up

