6.9 Treatment of Overdose

In the event of an overdose of $> 10\%$ of enfortumab vedotin, the site should notify the sponsor as soon as they are aware of the overdose. The subject should be closely monitored for adverse reactions. Supportive care per institutional standards should be administered.

For this study, an overdose of pembrolizumab will be defined as any dose of 1000 mg or greater. No specific information is available on the treatment of overdose of pembrolizumab. In the event of overdose, the subject should be observed closely for signs of toxicity. Appropriate supportive treatment should be provided if clinically indicated.

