10.3 Major Protocol Deviations

A protocol deviation is generally an unplanned excursion from the protocol that is not implemented or intended as a systematic change. All deviations from the protocol are to be recorded. A protocol waiver is a documented prospective approval of a request from an investigator to deviate from the protocol. Protocol waivers are strictly prohibited.

The investigator is responsible for ensuring the study is conducted in accordance with the procedures and evaluations described in this protocol and must protect the rights, safety and well-being of subjects. The investigator should not implement any deviation from, or changes of, the protocol, unless it is necessary to eliminate an immediate hazard to subjects.

A major protocol deviation is one that may potentially impact the completeness, accuracy or reliability of data contributing to the primary endpoint or affect the rights, safety or well-being of a subject. Major protocol deviations will have additional reporting requirements.

When a major deviation from the protocol is identified for an individual subject, the investigator or designee must ensure the sponsor is notified. The sponsor will follow-up with the investigator, as applicable, to assess the deviation and the possible impact to the safety and/or efficacy of the subject to determine subject continuation in the study.

The major protocol deviation criteria that will be summarized at the end of the study are as follows:

PD1 - Entered into the study even though the subject did not satisfy entry criteria

PD2 - Developed withdrawal criteria during the study and was not withdrawn

PD3 - Received wrong treatment or incorrect dose. For enfortumab vedotin, incorrect dose will be defined as less than or greater than 10% from the intended dose. For pembrolizumab, any dose of 1000 mg or greater will be considered incorrect dose.

PD4 - Received excluded concomitant treatment

The investigator will also assure that deviations meeting IRB/IEC and appropriate regulatory authorities' criteria are documented and communicated appropriately. All documentation and communications to the IRB/IEC and appropriate regulatory authorities will be provided to the sponsor and maintained within the Trial Master File.

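### Cohort 9: the only stated incorrect-dose criterion for pembrolizumab starts at 1000 mg, five times the fixed 200 mg dose, and has no lower bound

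*SAP*

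**What the plan says.** - **Incorrect dose.** SAP 6.2.2, item PD3, gives one numerical criterion for pembrolizumab: "any dose of 1000 mg or greater will be considered incorrect dose". Protocol 10.3 matches it: "For pembrolizumab, any dose of 1000 mg or greater will be considered incorrect dose".
- **Major noncompliance.** Protocol 6.4: "Dosing noncompliance for pembrolizumab of 1000 mg or greater will be considered a major protocol deviation".
- **Overdose.** Protocol 6.9 uses the same number for a different purpose: "an overdose of pembrolizumab will be defined as any dose of 1000 mg or greater".
- **Planned dose.** Protocol 6.1.2: "Pembrolizumab will be administered as a dose of 200 mg using a 30-minute intravenous infusion". On presentation: "Each vial contains 100 mg of pembrolizumab in 4 mL of solution".
- **Reduction.** Protocol 6.6.2.1: "The dose of pembrolizumab should not be reduced". SAP 6.5.1 also rules it out.
- **The partner drug.** The same PD3 item holds enfortumab vedotin to a two-sided limit of 90% to 110% of the intended dose.
- **Exposure summaries.** For pembrolizumab, SAP 6.3.2 plans duration, number of cycles, cumulative dose and interruptions. Enfortumab vedotin also gets dose intensity, relative dose intensity and dose-reduction counts.

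**The concern.** PD3 is meant to count subjects who received a dose other than the one intended. For a fixed dose that may not be reduced, any administered amount that differs materially from 200 mg is a departure from the regimen. The stated pembrolizumab criterion cannot detect an underdose of any size, and it ignores overdoses until they reach five times plan. One vial (100 mg) or a doubled dose (400 mg) meets no stated PD3 criterion.

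Two features suggest that a safety threshold was carried into a compliance rule. The number is identical to the overdose definition. And the weight-based drug, which has three permitted reduction levels, gets a tight two-sided band, while the fixed-dose drug gets a one-sided limit at 500% of plan, with no reason given.

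Two things are at stake. The cohort 9 deviation table would understate departures from the combination under evaluation, with its two components held to very different standards. And under protocol 10.3 a major deviation requires the sponsor to be notified and to assess whether the subject continues; the explicit rule does not trigger this for plausible vial errors.

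**Working it through.** No sample size, power or alpha figure is involved. The check compares the threshold with the planned dose.

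**Inputs.** Threshold 1000 mg (SAP 6.2.2; protocol 6.4, 10.3). Planned dose 200 mg and vial size 100 mg (protocol 6.1.2). Enfortumab vedotin tolerance 10% either way (SAP 6.2.2).

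**Threshold against plan.** 1000 / 200 = 5 times the planned dose, an excess of (1000 − 200) / 200 = 400%. In vials: 1000 / 100 = 10, against 200 / 100 = 2 planned.

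**A 10% rule applied to 200 mg.** 0.9 × 200 = 180 mg and 1.1 × 200 = 220 mg.

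| Administered dose (mg) | % of plan | Meets PD3 as stated | Outside 180–220 mg |
|---|---|---|---|
| 50 | 25 | no | yes |
| 100 | 50 | no | yes |
| 200 | 100 | no | no |
| 300 | 150 | no | yes |
| 400 | 200 | no | yes |
| 800 | 400 | no | yes |
| 999 | 499.5 | no | yes |
| 1000 | 500 | yes | yes |

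The wrong whole-vial amounts below the threshold are 1 vial and 3 to 9 vials, that is 100, 300, 400, 500, 600, 700, 800 and 900 mg. The stated rule flags 0 of these 8; a 10% band flags all 8. A wholly omitted dose is left out of this count because it is handled as an interruption.

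**Alternative reading of protocol 6.4.** If noncompliance of 1000 mg means a difference of 1000 mg from plan, the limit becomes 200 + 1000 = 1200 mg. There is still no lower bound.

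**Whether the exposure tables fill the gap.** Cumulative dose can hide offsetting errors: over six cycles, 4 × 200 + 100 + 300 = 1200 mg, the same as 6 × 200 mg. Where errors do not offset, the cohort summary dilutes them: a single 100 mg dose given in place of 200 mg to one of 40 subjects lowers the mean cumulative dose by 100 / 40 = 2.5 mg. No planned summary counts subjects who received a wrong amount.

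**The case against.** The strongest reply is that wrong doses are captured elsewhere. Protocol 10.3 says "All deviations from the protocol are to be recorded" and has a general, qualitative definition of a major deviation. Protocol 7.3.7 and 12.4.6.2 refer wrong doses and medication errors to 10.3 without naming a threshold. Protocol 6.4 has every dose entered on the eCRF, and 9.3.5 has all exposure data listed. This stands in part: such errors are not invisible, and a serious one could still be judged major. But both referrals lead back to the section that holds the 1000 mg rule, and recording a deviation does not place it in the PD3 count.

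A second reply is that PD3 opens in general terms and says only that doses from 1000 mg up are considered incorrect, without saying that smaller errors are acceptable. That reading is possible, so describing 1000 mg as the sole trigger is an interpretation. No other pembrolizumab dose criterion is stated, however, and a programmed table would follow the one that is.

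A third is that protocol 4.2.2 reports flat dose- and exposure-efficacy relationships over roughly a 5- to 7.5-fold exposure range, so moderate overdoses may matter little. That bears on the efficacy consequence of an overdose. It does not make an unplanned dose a correct one, and it offers nothing on 100 mg.

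Finally, the count of 8 amounts is not an expected error rate, and the documents supply no frequency. That is correct.

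**Conclusion.** The concern holds. As written, PD3 and the explicit major-noncompliance rule use an overdose limit to judge pembrolizumab dosing compliance. The limit lies at 5 times plan and has no lower bound, so administered doses above 0 and below 1000 mg that differ from 200 mg meet no stated criterion.

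The conclusion assumes that the stated number is applied as the operative criterion. The 8-of-8 contrast further assumes whole-vial errors and borrows the plan's own 10% rule as the comparison.

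The consequence is limited to deviation reporting and escalation in cohort 9. The analysis sets, the confirmed ORR and the stopping boundaries do not use PD3, so none of them changes. The rule should be corrected, but it does not threaten the trial's conclusions.

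**What to change.** Keep 1000 mg in protocol 6.9 as the overdose definition, where it also serves the event-of-clinical-interest reporting in 7.3.6. In protocol 6.4 and 10.3 and in SAP 6.2.2 (PD3), define an incorrect pembrolizumab dose as one outside a stated two-sided tolerance of the intended 200 mg. A 10% tolerance (below 180 mg or above 220 mg) would match the rule for enfortumab vedotin. Add an explicit exception for infusions stopped or not completed under the infusion-reaction rules in protocol Table 10, since those follow the protocol.

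The cost is wording edits in three places and one programmed check on dose data already on the eCRF, with slightly more deviations reported. Dosing, eligibility and the efficacy analyses stay as they are.

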6.2.3 Demographic and Other Baseline Characteristics

Demographic and other baseline characteristics will be summarized descriptively by cohort and overall for FAS and RES.

Demographic characteristics:

- Age, Age categories (< 65 years, ≥ 65 to < 75 years, ≥ 75 years), EudraCT age categories (≥ 18 to ≤ 64 years, ≥ 65 to ≤ 84 years, ≥ 85 years)
- Sex
- Ethnicity
- Race
- Region (North America, Asia)
- Baseline Height
- Baseline weight, baseline weight groups (≤ 100 kg, > 100 kg)
- Baseline BMI, baseline BMI categories (< 18.5, ≥ 18.5 to < 25, ≥ 25 to < 30, ≥ 30)

Baseline characteristics:

- Baseline measurable disease (Yes, No)
- Nectin-4 IHC H-score (including 25th percentile and 75th percentile)
- Baseline PD-L1 IHC status (PD-L1 low, PD-L1 high as defined in Table 2)
- ECOG PS (0, 1, > 1)
- Hemoglobin, Hemoglobin categories (< 10 g/dL, ≥ 10 g/dL)
- Albumin, Albumin categories (< LLN, ≥ LLN)
- HbA1C, HbA1C categories (≤ 5.6%, 5.7 to < 6.5%, ≥ 6.5%)
- Fasting glucose, fasting glucose CTCAE grade
- Total cholesterol, total cholesterol categories (low, normal, high)
- Baseline hepatic function group

Baseline hepatic function group is defined per the NCI-ODWG criteria based on total bilirubin and AST at the baseline as follows:

Normal:	total bilirubin ≤ ULN and AST ≤ ULN
Mild dysfunction:	(ULN < total bilirubin ≤ 1.5×ULN) or (AST > ULN and total bilirubin ≤ ULN)
Moderate dysfunction:	1.5×ULN < total bilirubin ≤ 3×ULN
Severe dysfunction:	total bilirubin > 3×ULN

- Baseline renal function group

Baseline renal function group is defined based on estimated creatinine clearance (CrCl) by Cockcroft-Gault formula.

Normal:	≥ 90 mL/min
---------	-------------

Mild insufficiency: ≥ 60 to < 90 mL/min

Moderate insufficiency: ≥ 30 to < 60 mL/min

Severe insufficiency: ≥ 15 to < 30 mL/min

End stage renal disease: < 15 mL/min

Cockcroft-Gault formula for estimating CrCl (mL/min):

$$\frac{[140 - \text{age}(\text{years})] \times \text{body weight (kg)} \times (0.85 \text{ if female})}{\text{serum creatinine (mg/dL)} \times 72}$$

- Baseline tobacco use
 - Prior tobacco history (never used, former smoker, current smoker, unknown)
 - Number of pack-years for current or former smoker
- History of diabetes/hyperglycemia defined as any hyperglycemia SSQ/CMQ

Disease specific history will be summarized descriptively by cohort and overall for FAS and RES.

- Time (months) since initial diagnosis of primary cancer
- $(\text{first dose date} - \text{date of initial diagnosis of primary cancer} + 1)/30.4375$
- Primary cancer type and location (location will be summarized for breast cancer, head and neck cancer and HNSCC only)
- Histological type at diagnosis
- Anatomic staging at screening
- Prior PD-L1 testing: Yes/No and test results
- Disease specific biomarkers:
 - For HR+/HER2- breast cancer (Cohort 1) and TNBC (Cohort 2): HER2 status and test method, ER status, PgR status, PIK3CA mutation status, BRCA mutation status
 - For squamous NSCLC (Cohort 3) and non-squamous NSCLC (Cohort 4): ALK rearrangement status and test method, EGFR status and test method, BRAF mutation status, NTRK fusion status, ROSI rearrangement status
 - For head and neck cancer and HNSCC: HPV status
 - For gastric or GEJ or esophageal cancer (Cohorts 6, 7, 8): HER2 status and test method, MSI status and test method, MMR status
- Brain metastases

Medical history other than primary cancer type and conditions existing at baseline will be coded in MedDRA and summarized by System Organ Class (SOC) and Preferred Term (PT) as well as by PT alone, by cohort and overall for FAS and other analysis populations if necessary. Baseline conditions are defined as those ongoing at the time of informed consent or arise following the time of informed consent and before the first dose of study drug. For ongoing medical conditions, Common Terminology Criteria for Adverse Events (CTCAE) grade will be provided in listing.

Number and percentage of subjects enrolled in each country and investigator site will also be presented.

6.2.4 Prior Systemic Anti-Cancer Therapy (for cohorts 1 to 8 only)

Prior systemic anti-cancer therapy will be summarized descriptively by cohort and overall for FAS and RES.

- Prior lines of systemic therapy (1 line, 2 lines, ≥ 3 lines)
- Prior lines of systemic therapy in metastatic setting (1 line, 2 lines, ≥ 3 lines)
- Type of prior systemic therapy (e.g., PD-L1/PD-1 inhibitor, platinum-based treatment, taxane, fluoropyrimidine containing therapy, targeted therapy, cetuximab, anthracycline, alkylating agent, hormonal therapy, PARP inhibitor, CDK 4/6 inhibitor) and subtype if applicable
- Setting of prior systemic therapy
- Setting of the most recent prior systemic therapy
- Relapse status (yes vs. no)
 - within 6 months after completion of cytotoxic therapy in neoadjuvant or adjuvant setting for HR+/HER2- breast cancer (Cohort 1), TNBC (cohort 2), and gastric or GEJ or esophageal cancer (Cohorts 6, 7, 8)
 - within 6 months after completion of platinum-based therapy in neoadjuvant or adjuvant setting for squamous NSCLC (Cohort 3), non-squamous NSCLC (Cohort 4), and head and neck cancer (Cohort 5)
- Best response to prior systemic therapy
- Best response to the most recent prior systemic therapy
- Reason for discontinuing the most recent prior systemic therapy
- Time since completion/discontinuation of the most recent prior systemic therapy

Setting of prior systemic therapy, best response to prior systemic therapy, reason for discontinuation, and time since completion/discontinuation of prior systemic therapy may be summarized by type of prior systemic therapy.

